3.3. Changes to Analysis from Protocol

The SAP supersedes the statistical methods described in the clinical study protocol. Analysis methods that summarize and evaluate study efficacy endpoints for statistical significance will be implemented as described in the SAP.

An additional exploratory analysis as in primary analysis will be performed stratified by baseline TNSS-3 ≤ 7 , TNSS-3 > 7 .

4. PLANNED ANALYSES

The following analyses will be performed for this study:

- Final Analysis

4.1. Data Monitoring Committee (DMC)

There will be no DMC for this study.

4.2. Interim Analysis

No interim analysis is planned.

4.3. Final Analysis

All final, planned analyses identified in this SAP will be performed by IQVIA Biostatistics following Sponsor Authorization of this Statistical Analysis Plan, Database Lock, Sponsor Authorization of Analysis Sets and Unblinding of Treatment.

Document:	[REDACTED]	
Author:	[REDACTED]	Version Number: [REDACTED]
		Version Date: [17Feb2023]
Template No.:	[REDACTED]	Reference: [REDACTED]
Effective Date:	[REDACTED]	
	[REDACTED]	

5. ANALYSIS SETS

5.1. Process for Analysis Set Assignment

The subjects will be assigned to the analysis sets programmatically as per the definitions below.

5.2. All Subjects Enrolled Set [ENR]

The all subjects enrolled (ENR) set will contain all subjects who provide informed consent for this study.

5.3. Intent-To-Treat Analysis Set [ITT]

The intent-to-treat analysis set (ITT) will contain all eligible subjects (passed screening and confirmation challenge) who have been allocated to a randomized treatment regardless of whether study drug wallet was used or not. Subjects will be classified according to randomized treatment.

5.4. Per Protocol Analysis Set [PPAS]

Not applicable.

5.5. Safety Analysis Set [SAF]

The safety analysis set (SAF) will contain all subjects in the ITT set who receive at least one dose of study medication and subjects will be classified according to treatment received.

If there is any doubt whether a subject was treated or not, they will be assumed treated for the purposes of analysis.

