7.1 Discontinuation of Study Drug

It may be necessary for a participant to permanently discontinue study drug if any of the following criteria are met:

- Important Protocol violation
- Withdrawal of consent by a participant
- Participant is lost to follow-up
- Inadvertent enrollment of a participant
- Pregnancy – see [Section 8.3.5](#)
- Termination of the study by the Sponsor

If study drug is permanently discontinued, the participant will remain in the study until EOS on D5. See [Section 1.3](#) for data to be collected at the time of discontinuation of study drug and follow-up and for any further evaluations that need to be completed.

If a participant who does not meet enrollment criteria is inadvertently enrolled, that participant must be discontinued from study drug and the Sponsor, or Sponsor designee, must be contacted. An exception may be granted in rare circumstances for which there is a compelling safety reason to allow the participant to continue. In these rare cases, the Investigator must obtain documented approval from the Sponsor, or Sponsor designee, to allow the participant to continue in the study.

Participants who discontinue study drug will not be replaced.

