9.2 Analysis Sets

For the purposes of analysis, the following analysis sets are defined:

- Safety population is defined as randomized participants who did receive at least one dose of study drug analyzed according to the treatment actually received.
- The intent-to-treat population will include eligible participants who have been allocated to a randomized treatment regardless of whether the study drug wallet was used or not.

- The mITT population will comprise all eligible, randomized, and treated participants with TNSS-3 evaluation at H0 at V4 and at least a further time point at V4 (main analysis population for the efficacy endpoints).

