9.3.5 Safety Analyses

All safety analyses will be performed on the Safety Analysis Set.

The pre-treatment period starts the day of the signed informed consent and ends before administration of study drug.

The treatment-emergent AE period starts at time of administration of study drug ends 3 days after administration of study drug.

All AEs diagnosed by the Investigator will be reported and described.

All AEs will be coded using the version of the Medical Dictionary for Regulatory Activities currently in effect with the Sponsor at the time of the considered database lock.

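### SAP 5.5 nests the safety set in an ITT set limited to eligible subjects, which Protocol 9.2 does not do, so a participant enrolled in error and dosed can be left out of the safety tables

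*SAP*

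**What the plan says.** The two documents define the safety population differently.

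- **Protocol 9.2:** "Safety population is defined as randomized participants who did receive at least one dose of study drug analyzed according to the treatment actually received". Eligibility is not a condition, and the definition does not refer to the ITT population. The protocol's ITT definition does carry the condition ("The intent-to-treat population will include eligible participants who have been allocated to a randomized treatment"), but safety is not built on it.
- **SAP 5.5:** "The safety analysis set (SAF) will contain all subjects in the ITT set who receive at least one dose of study medication", classified by treatment received.
- **SAP 5.3:** the ITT set "will contain all eligible subjects (passed screening and confirmation challenge) who have been allocated to a randomized treatment".

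Four other provisions matter.

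- Protocol 7.1 foresees enrolment in error: "If a participant who does not meet enrollment criteria is inadvertently enrolled, that participant must be discontinued from study drug". It also allows, in rare cases and with documented sponsor approval, that such a participant continues.
- Protocol 7.1 keeps people who stop drug under observation: "If study drug is permanently discontinued, the participant will remain in the study until EOS on D5".
- SAP 5.1 assigns subjects to sets by program from the written definitions.
- SAP 3.3 says that the SAP overrides the protocol's statistical methods. The only specific change it lists is an added exploratory analysis by baseline TNSS-3.

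**The concern.** A safety population normally includes everyone exposed, because an adverse event after dosing is informative whether or not the person should have been enrolled. Protocol 9.2 follows that principle. By going through ITT, the SAP adds eligibility as a third condition without saying so. Since the SAP governs and sets are derived by program, the narrower definition is the one that would be implemented.

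The outputs at stake are wide in scope. Protocol 9.3.5 says "All safety analyses will be performed on the Safety Analysis Set", and SAP 18 rests all safety outputs on one set. The SAP also uses the SAF for protocol deviations (9.2), medical history (11), concomitant medication (13), exposure (14) and compliance (15). The deviation table is the most awkward of these: a participant randomised in breach of the entry criteria would be missing from the table where readers would look for that breach.

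**Working it through.** No power or sample-size figure bears on this point, so the check is a comparison of definitions.

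**Step 1. Write out the sets.**

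- Protocol 9.2 safety population = randomised AND dosed.
- SAP 5.3 ITT = eligible AND randomised.
- SAP 5.5 SAF = ITT AND dosed = eligible AND randomised AND dosed.
- Protocol set minus SAP set = randomised AND dosed AND not eligible.

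**Step 2. Ask whether the difference can contain anyone.** Protocol 7.1 provides for participants enrolled without meeting the criteria. They remain in the study to Day 5 after stopping drug, or exceptionally continue, so safety data on them can exist. The difference can be non-empty.

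**Step 3. Sort the cases**, using the SAP 5.3 explanation of *eligible*.

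| Randomised and dosed participant | Protocol 9.2 | SAP 5.5 as written |
|---|---|---|
| Did not reach the Visit 2 TNSS-3 threshold | In | Out |
| Failed a screening criterion, error found later | In | Out |
| Passed Visits 1 and 2, first met an exclusion at Visit 3 or 4 | In | Probably in |

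The re-check of exclusion criteria at Visit 4 (Protocol Table 1, footnote a) comes after the Day 2 and Day 3 home doses. It matters here only when it uncovers an error dating back to Visit 1 or 2.

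**Step 4. Look for a rule that puts the person back.** SAP 5.5 treats doubtful cases as treated, but that concerns dosing, not eligibility. SAP 9.1 summarises reasons for exclusion from each analysis set in all consented subjects, so the person is visible there, but it does not return them to a SAF table.

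**Step 5. Scale.** The documents give no rate of enrolment in error, so the count k is purely an assumption. Assume also that all 96 planned participants are randomised and dosed. Share of the denominator lost = k/96.

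- k = 0: SAF 96, nothing lost, and the two definitions coincide.
- k = 1: SAF 95, 1/96 = 1.0%.
- k = 2: SAF 94, 2/96 = 2.1%.
- k = 3: SAF 93, 3/96 = 3.1%.

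With the SAF defined as in Protocol 9.2, it is 96 in every row.

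**The case against.** The strongest defence is that *eligible* does no work in SAP 5.3. It is explained as having passed screening and the challenge, and Protocol 5.4 defines a screen failure as a consenting participant who is not then randomised. On that reading nobody randomised is a screen failure, and a program keyed to recorded screening status could keep everyone in ITT and in the SAF. This shows that the wording can be implemented in two ways. It does not remove the conflict. Both documents list eligibility separately from allocation when they define mITT (Protocol 9.2, SAP 5.6), and Protocol 7.1 recognises enrolled people who do not meet the criteria. Two readings that give two safety sets are themselves a defect when assignment is by program.

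Other parts of the defence stand and limit the point.

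- Events would not vanish from the trial. SAEs go to the sponsor within 24 hours (Protocol 8.3.1) and AESIs require immediate notification (Protocol 8.3.6), whatever the analysis set. The loss is confined to SAF-based outputs.
- SAP 4.3 requires sponsor authorisation of the analysis sets before the final analysis, so the omission might be noticed. That is a chance to catch it, not a rule that corrects it.
- Eligibility is checked at Visits 1, 2 and 3 before any dose, and Protocol 5.0 bars waivers. Few or no cases may arise.
- Safety is descriptive, and the efficacy analyses use mITT, which both documents already limit to eligible participants. The efficacy conclusion is untouched.

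**Conclusion.** Wrong as written, at minor to moderate severity. The SAP's safety set contradicts the protocol's, the SAP takes precedence, and the change is not declared. The consequence depends on three things happening together: a participant is randomised despite failing a screening criterion or the Visit 2 threshold, that participant is dosed, and the strict reading is programmed. It also assumes that the set printed as SAE in SAP 18 means the SAF, which Protocol 9.3.5 supports.

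A reader might infer three stronger things that the documents do not support.

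- *That anyone found ineligible at Visit 4 is dropped.* On the SAP 5.3 wording, a person who had passed Visits 1 and 2 most likely stays.
- *That the omission makes the drug look safer.* Nothing in the documents shows that people enrolled in error have more adverse events. The clearest excluded case, someone below the Visit 2 symptom threshold, reacted less to the challenge. The direction of any bias is unknown.
- *That a particular number will be affected.* The counts under the check are illustrations, and zero is entirely possible.

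What remains is a small expected effect that is all-or-none for each person. If one such participant had an AESI, the SAF tables would omit it, although it would have been reported to the sponsor.

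**What to change.** Redefine the SAF in SAP 5.5 as every randomised subject given one or more doses of study medication, whether or not the entry criteria were met, grouped by treatment received, and delete the link to the ITT set. This restores Protocol 9.2 and removes the need to decide what *eligible* means for safety. ITT and mITT can stay as they are, so no efficacy analysis changes.

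If the sponsor does intend the narrower set, SAP 3.3 should list and justify it as a change from the protocol.

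The cost is one sentence in the SAP before database lock and unblinding. No extra data, participants or assessments are needed.

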5.6. Modified Intent-To-Treat Analysis Set [mITT]

The modified intent-to-treat analysis set (mITT) will contain all eligible, ITT, and treated subjects with Total Nasal Symptoms Score of 3 symptoms (TNSS-3) evaluation at H0 at V4 and at least a further time point at Visit 4. Subjects will be classified according to randomized treatment.

Document:	[REDACTED]	
Author:	Version Number:	[REDACTED]
	Version Date:	[17Feb2023]
Template No.:	Reference:	[REDACTED]
Effective Date:	[REDACTED]	
[REDACTED]		

6. GENERAL CONSIDERATIONS

6.1. Reference Start Date and Study Day

Study Day will be calculated from the reference start date and will be used to show start/stop day of assessments and events. It will appear in every listing where an assessment date or event date appears.

Reference start date is defined as the day of randomization (Day 1 is the day of randomization).

- If the date of the event is on or after the reference date, then:
- Study Day = (date of event – reference date) + 1.
- If the date of the event is prior to the reference date, then:
- Study Day = (date of event – reference date).

In the situation where the event date is partial or missing, the date will appear partial or missing in the listings, and Study Day, and any corresponding durations will be presented based on the imputations specified in APPENDIX 2; Partial Date Conventions.

6.2. Baseline

Unless otherwise specified, baseline is defined as the last non-missing measurement taken prior to reference start date (including unscheduled assessments). Baseline of the symptoms scoring will be H0 at visit 4 value according to the analysis.

6.3. Derived Timepoints

Not applicable.

6.4. Unscheduled Visits and Early Termination Data

In general, for by-visit summaries, data recorded at the nominal visit will be presented. Unscheduled measurements will not be included in by-visit summaries.

Listings will include scheduled, unscheduled, and early discontinuation data.

Document:	[REDACTED]	
Author:	[REDACTED]	Version Number: [REDACTED]
		Version Date: [17Feb2023]
Template No.:	[REDACTED]	Reference: [REDACTED]
Effective Date:	[REDACTED]	
[REDACTED]		

6.5. Windowing Conventions

No visit windowing will be performed for this study.

6.6. Statistical Tests

The default significant level will be (5%); CIs (confidence intervals) will be 95% and all tests will be two-sided, unless otherwise specified in the description of the analyses.

6.7. Common Calculations

For quantitative measurements, change from baseline will be calculated as:

- Test Value at Visit X – Baseline Value

6.8. Software Version

All analyses will be conducted using SAS version 9.4 or higher.

7. STATISTICAL CONSIDERATIONS

Unless otherwise specified, all statistical tables will be provided by treatment group and will first present the results in the active group (FEXPRESAR) and then the results in the placebo group. The column ‘overall’ displaying all patients (all treatment groups combined) will be presented where appropriate.

The descriptive summary for continuous data will include the number of non-missing observations (n), mean, standard deviation, median, 25th percentile and 75th percentile, minimum, and maximum. The number of subjects with missing data will be displayed when relevant.

Categorical data will be summarized for each treatment group using counts (n) and percentages (%). The number of subjects with missing data will be displayed when relevant, but it will not be included in the denominator for the calculation of percentages unless otherwise specified.

If the original data has N decimal places, then the summary statistics will have the following decimal places:

- Minimum and maximum: N
- Mean, median, percentiles, confidence intervals, ratios: N + 1

Document:	[REDACTED]	
Author:	Version Number:	[REDACTED]
	Version Date:	[17Feb2023]
Template No.:	Reference:	[REDACTED]
Effective Date:		[REDACTED]
[REDACTED]		

- SD: N + 2

Percentages will be reported to one decimal place. P-values should be reported to three decimal places, except values <1.000 but >0.999 will be presented as ‘>0.999’ (e.g., 0.9998 is presented as >0.999); and values <0.001 will be presented as ‘<0.001’ (e.g., 0.0009 is presented as <0.001)

7.1. Adjustments for Covariates and Factors to be Included in Analyses

The following covariates and factors are used in the analyses. For details of their inclusion in the models, see the specific analysis section.

- TNSS-3 at Day 1/Visit 4 H0
- (Total Ocular Symptoms Score) TOSS at Day 1/Visit 4 H0
- (Total Symptoms Score) TSS at Day 1/Visit 4 H0
- Individual symptoms score at Day 1
- Treatment group (Fexofenadine 180 mg, Placebo)
- Time point (H0 to H12)
- Treatment group by time point
- Stratification factor – Visit 2 TNSS-3 (TNSS-3 ≤7, TNSS-3 >7)

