6.3 Measures to Minimize Bias: Randomization and Blinding

6.3.1 Randomization

The subject randomization list will be supplied to the study site by the clinical research organization (CRO).

Day 1 to Day 3 (double-blind, placebo-controlled part):

All participants will be centrally assigned to randomized study drug at Visit 3 (Day 1) as per the randomization list. The study site staff will record the subject number allocated at the time of screening and wallet number in the electronic case report form (eCRF). After the individual study drug wallets are assigned, the dispensing staff can ensure their numbers are correct and the participant has not already been randomized. Individual study drug wallets (containing 3 tablets of either fexofenadine or placebo – 2 doses and 1 additional tablet in case of loss) will be dispensed to the participants as assigned. The participants will be instructed by the study staff, to consume 1 tablet of study drug, each on Day 2 and Day 3 at home. The participant will return the used study drug wallet (containing 1 remaining tablet) when they return to the study site on Day 4, before the pollen challenge. Returned study drug should not be re-dispensed.

Day 4 (open-label part, post pollen challenge):

The participants will be exposed to a 3-hour pollen challenge at Visit 4 (Day 4). The study site staff will provide a commercial pack of fexofenadine 180 mg to each participant and instruct the participants to consume only one tablet from the pack. At H3, post pollen challenge, each participant will take the study drug at exactly the same time in the EEU. This time point will be recorded by study staff. The commercial pack of fexofenadine 180 mg with remaining tablets will be returned to the study site staff by each participant before leaving the EEU after completing all assessments at H6.

Stratification

Participants will be randomized to study drug at Visit 2. Stratification of TNSS-3 ≤ 7 /TNSS-3 > 7 will be documented in the Statistical Analysis Plan (SAP).

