9.5 Sample Size Determination

Number of subjects (N) = 96 randomized participants (86 evaluable participants)

All eligible participants will be randomized into 1 out of 2 Arms with the randomization ratio allocation 1:1 as follows:

- Arm A: two days of pre-treatment with fexofenadine, then fexofenadine 180 mg during the test pollen challenge.
- Arm B: two days of pre-treatment with placebo, then fexofenadine 180 mg during the test pollen challenge.

The primary efficacy endpoint is the AUC of TNSS-3 (including rhinorrhea, sneezing, and nasal itching, where each symptom is scored from 0 to 3) from H0 to H6 at Visit 4. The maximum score of TNSS-3 is 9.²

The expected benefit of the pre-treatment or the variability of the pre-treatment using the AUC of the TNSS-3 were not published in the literature when the pre-treatment with fexofenadine before allergen exposure has been evaluated.²⁰ Therefore, given the previous study LPS15332 using TNSS-3, the mean (SD) of the AUC_{h2-h12} of the TNSS-3 has been estimated to be equal to 26.34 (16.66) on the placebo group and 18.53 (13.73) on the fexofenadine group after 3 hours of pollen exposure in the period 3, thus a common SD, estimated to be equal to 15, has been used for the sample size calculation.¹⁴ An MCID is commonly defined as a 0.55 change on Total Nasal Symptoms Score of 4 symptoms (TNSS-4) when 4 individual symptoms (ie, rhinorrhea, nasal congestion, nasal itching, and sneezing) are measured.¹⁶

Assuming a common SD=15 and a targeted effect size of 0.70 for the primary endpoint, it will correspond to a difference of AUC of TNSS-3 between Arm A and Arm B of 10.5, which may be interpreted as a difference of TNSS-3 around 2 points between 2 Arms at each time point (which is higher than the MCID of TNSS-3 with 3 individual symptoms). Therefore, at least 86 evaluable patients in both, Arm A and B (ie, included in the mITT population, meaning 43 patients in each arm) are needed to detect a 0.70 effect size for the additional benefit of two days of pre-treatment with fexofenadine on the SAR symptoms with 90% of power and a 2-sided type I error of 5%, using a 2-sample t-test which is assumed to be roughly equivalent

to the primary analysis that will be planned. This sample size has been calculated using EAST6.5 software.

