16.1.3. Primary Analysis of Primary Efficacy Variable(s)

The primary efficacy analysis will be performed for the mITT.

The primary analysis will be the comparison of the primary efficacy endpoint (ie, AUC of the TNSS-3 from H0 to H6 at V4) between fexofenadine and placebo, using an analysis of covariance (ANCOVA) with treatment group as fixed effect and the baseline value of TNSS-3 (i.e., at H0 at V4) as covariate. The mean TNSS-3 and its 95% CI will be plotted across time from H0 to H6 at Visit 4. This plot will also include the LS mean and 95% CI of the AUC.

Document:	[REDACTED]	
Author:	Version Number:	[REDACTED]
	Version Date:	[17Feb2023]
Template No.:	Reference:	[REDACTED]
Effective Date:		[REDACTED]
[REDACTED]		

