16.2.3. Analysis of Secondary Efficacy Variables

16.2.3.1. ANALYSIS OF SECONDARY VARIABLES BASED ON AUC

All secondary endpoints based on the AUC (i.e., TNSS-3 and TOSS) will be analysed using an ANCOVA model,

Document:	[REDACTED]	
Author:	Version Number:	[REDACTED]
	Version Date:	[17Feb2023]
Template No.:	Reference:	[REDACTED]
Effective Date:	[REDACTED]	
[REDACTED]		

with treatment group as fixed effect and the baseline values as covariate. For the AUC assessment starting from Randomization (D1) to D4, symptom scoring at D1 will be used as baseline.

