16.2.3.2. ANALYSIS OF TNSS-3, TOSS, AND TSS

The TNSS-3, TOSS, TSS, and individual symptom score by time point will be analysed given the mean and 95% confidence interval (CI).

The TNSS-3, TOSS, and TSS will be analysed using MMRM (Mixed Models for Repeated Measures), with treatment, time point and treatment group by time point interaction as fixed effect with their respective H0 scores as baseline covariate. The MMRM model will be run using PROC MIXED procedure with an unstructured correlation matrix to model the within-subject errors. If unstructured fails to converge, the following covariance structures will be tested: CS (compound symmetric) first, and then AR (1) (first-order autoregressive). Denominator degrees of freedom will be estimated using the Satterthwaite's approximation.

The descriptive statistics (number, mean, SD, median, Q1 and Q3, minimum, and maximum) of AUC and the statistics from the MMRM, least square (LS) means, standard errors (SEs) and 95% confidence intervals (CIs)) will be provided.

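### The Visit 2 TNSS-3 stratification factor is listed in SAP 7.1 but left out of the primary ANCOVA, the secondary AUC ANCOVAs and the MMRM

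*SAP*

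**What the plan says.** **Stratification.** Protocol 6.3.1, in a paragraph on stratification within the randomisation section, says "Stratification of TNSS-3 ≤ 7 /TNSS-3 > 7 will be documented in the Statistical Analysis Plan (SAP"). SAP 7.1 names the factor, "Stratification factor – Visit 2 TNSS-3 (TNSS-3 ≤7, TNSS-3 >7"), and refers the reader to the individual analysis sections for which model uses what. The SAP does not state that the randomisation list is stratified by this factor.

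**Models.**
- Primary AUC of TNSS-3, H0 to H6 (SAP 16.1.3): "using an analysis of covariance (ANCOVA) with treatment group as fixed effect and the baseline value of TNSS-3" at Visit 4 H0.
- Secondary AUCs (SAP 16.2.3.1): "with treatment group as fixed effect and the baseline values as covariate".
- MMRM for TNSS-3, TOSS and TSS (SAP 16.2.3.2): "with treatment, time point and treatment group by time point interaction as fixed effect with their respective H0 scores as baseline covariate".

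Protocol 9.3.2 and 9.3.3 describe the same models.

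**Other uses of the ≤7 / >7 split.** SAP 3.3 adds an exploratory version of the primary analysis, stratified by what it calls baseline TNSS-3. SAP 6.2 sets the symptom-score baseline at Visit 4 H0, whereas SAP 10 attaches the same cut to Visit 2, as bands 4–7 and 8–9. The exploratory sections of the SAP are redacted.

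**Timing of randomisation.** Protocol 6.3.1 says both "All participants will be centrally assigned to randomized study drug at Visit 3 (Day 1) as per the randomization list" and "Participants will be randomized to study drug at Visit 2".

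**The concern.** Stratified allocation balances the arms on the stratum, so the treatment difference varies less from trial to trial than under simple randomisation. An analysis without the stratum does not see this. Whatever the stratum explains stays in the residual variance, so the reported standard error exceeds the true one. The interval is then too wide and the test is conservative.

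The design gives a reason to expect some prognostic value. The Visit 2 score is the response to a 3-hour ragweed challenge at the same target concentration as at Visit 4. The Visit 4 H0 covariate is taken at the start of exposure, outside the pollen season and after a washout of at least 15 days. It need not capture how strongly a participant reacts to the challenge. This is an argument from the design; the documents give no estimate.

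The protocol leaves the documentation of stratification to the SAP, and the SAP supplies only a label. That gap remains whatever the size of the effect.

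**Working it through.** **Inputs from Protocol 9.5.** SD 15, effect size 0.70 (difference 0.70 × 15 = 10.5), two-sided 5%, 90% power, 1:1 allocation, 43 evaluable per arm, 10% dropout.

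**The plan's own figure.** The sample size was obtained "using a 2-sample t-test which is assumed to be roughly equivalent" to the primary analysis.
- n per arm = 2 × (1.960 + 1.282)² / 0.70² = 42.9, so 43 per arm and 86 in total. This reproduces.
- 86 / 0.90 = 95.6, so 96 randomised. This reproduces.
- The noncentral t distribution gives 89.4% power at 43 per arm, so the planned 90% holds to within rounding.

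**Assumptions not in the documents.** R² is the share of the AUC variance left after Visit 4 H0 TNSS-3 that the Visit 2 stratum explains, taken as 0, 0.05, 0.10 or 0.20. In the simulation, 30% of participants are in the upper stratum (50% gave the same results within simulation error), and allocation is in permuted blocks of 4 within stratum.

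**Formulas, stratified allocation, stratum omitted.**
- Model SE / SE with the stratum = 1/√(1 − R²). The excess is 0, 2.6, 5.4 and 11.8%.
- Type I error = 2 × [1 − Φ(1.96/√(1 − R²))]. At R² = 0.10, 1.96/0.949 = 2.066, which gives 0.039. Over the range: 0.050, 0.044, 0.039, 0.028.
- 95% CI width with residual SD 15: 2 × 1.989 × 15 × √(2/43) = 12.9 without the stratum. Multiplying by √(1 − R²) gives 12.9, 12.5, 12.2 and 11.5 with it.

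**Simulation.** 60,000 trials per setting, 43 per arm, with Visit 4 H0 TNSS-3 in both models and the effect size of 0.70 applied to the SD remaining after that covariate.

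| Assumed R² | 0 | 0.05 | 0.10 | 0.20 |
|---|---|---|---|---|
| Type I error, stratum omitted | 4.8% | 4.4% | 3.9% | 2.9% |
| Type I error, stratum included | 4.8% | 4.9% | 5.0% | 5.0% |
| Power, omitted | 89.0% | 89.6% | 89.9% | 91.4% |
| Power, included | 89.0% | 90.5% | 91.8% | 94.6% |
| Gain in power (points) | 0 | 0.9 | 1.9 | 3.2 |
| 95% CI width, included (12.9 omitted) | 12.9 | 12.6 | 12.3 | 11.6 |

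The Monte Carlo error is about 0.09 points for type I error and 0.12 for power. The simulated widths are up to 0.1 above the formula, which assumes exact balance within strata.

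**If allocation is not stratified.** Type I error without the stratum stays at 4.8–5.1%. Adding the stratum changes power from 89.1 to 88.7%, 88.9 to 90.1%, 89.2 to 91.8% and 89.2 to 94.3%, that is by −0.4, +1.2, +2.6 and +5.1 points. A prognostic stratum therefore gains precision under either form of allocation.

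**The case against.** **SAP 7.1 makes no promise for any one model.** It is a pooled list that defers to the analysis sections, and other listed items, such as time point, are also absent from the primary ANCOVA. The factor has a visible use in SAP 3.3 and may have more in the redacted sections. The primary model is specified in advance and agrees between protocol and SAP. All of this is correct, so no commitment is broken. It remains true that none of the primary, secondary or MMRM models reflects the stratum.

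**The effect is conditional and probably small.** It needs stratified allocation and a stratum that predicts beyond H0, and the documents establish neither. At R² of 0.05 to 0.10 the gain is one or two points of power. This stands, and the figures for R² = 0.20 are an upper illustration.

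**The power gains may be overstated.** Protocol 9.5 ties 0.70 to an SD of 15 for an unadjusted t-test, so it can be read as relative to the marginal SD. If the H0 covariate itself explains variance (coefficient 0.5 and unit variance, as simulated), the effect on the residual scale is 0.70 × √1.25 = 0.78. Power is then about 95% or more either way, and the gain at R² of 0.05, 0.10 and 0.20 is roughly 0.3 to 1.4 points. This is fair. The type I error and the proportional narrowing of the interval do not depend on it.

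**Only a single-outcome ANCOVA was computed.** That is so. For TOSS, the Day 1 to Day 4 AUCs and the MMRM the mechanism is the same, but the size is unquantified and probably smaller for TOSS and the Day 1 to Day 4 AUCs.

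**A stratum as randomised does not exist if the list is unstratified.** This is correct, and the recommended wording has to cover both cases.

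**Conclusion.** The point holds as one of efficiency and consistency. It does not threaten validity. All three model descriptions omit a factor that the SAP itself calls a stratification factor, and the SAP does not settle whether allocation is stratified. Under stratified allocation the omission makes the primary test conservative and its interval up to about 12% wider than with the stratum, for R² up to 0.20. At R² = 0 nothing is lost. Under unstratified allocation the test keeps its size and only precision is forgone.

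Confidence in the size is moderate, because the partial R² is assumed throughout. The change is still worth making. It is nearly free, helps under either form of allocation if the stratum is prognostic, and is credible only if made before unblinding.

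**What to change.** Before unblinding:

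1. State in the SAP whether the randomisation list is stratified by Visit 2 TNSS-3 (≤7 / >7), as Protocol 6.3.1 says the SAP will document.
2. Add the stratum as a fixed effect to the primary ANCOVA (SAP 16.1.3) and, for consistency, to the secondary AUC ANCOVAs (16.2.3.1) and the MMRM (16.2.3.2). Use the stratum as randomised if the list is stratified, and otherwise the recorded Visit 2 band.
3. In SAP 3.3, replace the reference to baseline TNSS-3 by the same Visit 2 stratum. SAP 10 supports that reading, but SAP 6.2 would lead a programmer to the Visit 4 H0 score.
4. Reconcile the Visit 2 and Visit 3 statements on the time of randomisation in Protocol 6.3.1. This is a separate drafting correction.

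The cost is SAP wording and one degree of freedom in each model, plus a clarification of the protocol text. No new data and no change in sample size are needed.
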